2.3 Study design

Study population and sample size

This study will determine the prevalence of genital HPV among males aged 17-19 years using two cross sectional samples, the first obtained over 2014-2015 (period 1) and the second over 2016-2017 (period 2) (Table 1). Given the differing age groups that will have been offered vaccination over the four years, period 1 will provide baseline prevalence among males prior to the vaccination program – a prevalence that reflects herd immunity from pre-existing vaccination of females. In period 1, most 17-19 year old males will not have been offered the vaccine (Table 1). By contrast, in period 2, most 17-19 year old males will have been offered vaccination as part of the male vaccination program (Table 1).

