2.4 Study flowchart

2.5 Study procedures

This study will recruit 17 to 19 year old males from universities and other sources including sexual health services. Potential participants will be identified by a nurse or doctor if they present to a health service or if they become aware of the study through advertising will discuss the study with a research nurse.

Eligibility criteria

- Male
- Aged 17 to 19*
- Residing in Australia from 12 years of age[#]
- Able to complete study requirements

Exclusion criteria

- Males who report sex with men in the past 12 months

*Must be aged 17, 18 or 19 years during the four year study period, that is, January 1 2014 through to December 30 2017.

[#]This is to ensure that males included in the study were present in Australia at the time HPV vaccination was offered.

Men who agree to the study will be asked to provide informed, written consent and undertake self-testing for genital HPV and a questionnaire will be obtained. Self-collection of the swab will be completed at the participants convenience using postal specimens that include a self-testing kit that is either given to participants attending services or posted out if recruitment is via advertising.

The questionnaire will capture:

- Demographic information such as age and education level.
- Detailed sexual history including: age at first sex; number and gender of sexual partners over different time periods; sexual practices including oral, anal and vaginal sex; and condom use.
- Relevant medical information such as history of genital warts, circumcision status, and smoking.

- History of previous HPV vaccination

HPV DNA sampling

Each man in the study will be asked to obtain a genital specimen which will be self-collected by participants using a swab on the glans penis, coronal sulcus, foreskin (if uncircumcised), and penis.

Laboratory testing for HPV DNA

Samples will be tested at the Regional HPV Labnet Reference Laboratory, Molecular Microbiology Department, Royal Women's Hospital, Melbourne. Cellular material will be pelleted in 1mL aliquots by centrifugation at 5,000 ×g and resuspended in 200 µL PBS. Total DNA will be extracted on the MagNA Pure 96 using the MagNA Pure 96 DNA and Viral NA small volume kit (Roche Diagnostics GmbH, Penzberg, Germany).

Extracted DNA will be pre-screened to assess its integrity by quantitative PCR amplification of a 260 base pair product of the human beta-globin gene.⁶

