2.7 Statistical analysis

The primary outcome of interest will be the change in prevalence of quadrivalent vaccine types (6, 11, 16 and 18) among 17-19 year old men in the two time periods. The study will also provide data on the change in prevalence of non-vaccine types.

The required sample size for each year is dependent upon the expected prevalence of genital HPV and affects the precision of the prevalence estimates (95% confidence intervals, CI) in the two cross sectional samples. Different prevalence rates and 95%CI are shown for various sample sizes in Table 1.

Table 1: Estimated 95% confidence intervals for differing HPV prevalent rates and sample sizes

HPV prevalence rate (%)	Sample size (persons)				
	100	200	300	400	500
5	0.0186-0.1183	0.0256-0.0927	0.0293-0.0829	0.0316-0.0774	0.0333-0.0739
10	0.0516-0.1804	0.0637-0.1523	0.0695-0.1411	0.0732-0.1347	0.0758-0.1305

Previous estimates of HPV infection have been determined by investigators in our group for females but are not available for males.⁴ A sample size of 200 males in each of the two periods would provide reasonable confidence intervals around expected prevalence rates for individual HPV types. This would require a total of 400 males for the entire four year study.

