2.13 Protocol Submission

This protocol has been submitted to MSD Australia.

Table 1: Age of boys who will be offered HPV vaccination via schools and community based programs by year, Victoria 2013-2017.*

Age	11	12	13	14	15	16	17	18	19	20	
2013											
2014											} Period 1 [#]
2015											
2016											} Period 2 [#]
2017											

*Dark grey squares indicate that boys within these age groups are currently being offered vaccination in the calendar year shown in the row. Light grey squares indicate the age of boys who have previously been offered vaccination for HPV in previous calendar years. Time limited vaccination of year 9 students and those aged 14 and 15 will occur in 2013 and 2014 only whereas ongoing vaccination will be offered to those in year 7 (which may include some 11 year olds) and those aged 12 and 13 years.

[#]The boxes with hatched lines indicate the age range of boys who will be recruited in Period 1 (2014-2015, n=200) and Period 2 (2016-2017, n=200).

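### Does the age footnote let in men outside 17-19, and could the same man be counted in both periods?

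*Combined protocol and SAP*

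**What the plan says.** Section 2.5 lists an age criterion of 17 to 19 with an asterisk. The footnote reads "Must be aged 17, 18 or 19 years during the four year study period" and gives the dates as 1 January 2014 to 30 December 2017. It mentions neither the consent date nor the swab date. On timing of the specimen, the same section says "Self-collection of the swab will be completed at the participants convenience" and sets no limit. The only exclusion is "Males who report sex with men in the past 12 months".

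Other places describe the population:

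- Section 2.3 sets out to estimate "prevalence of genital HPV among males aged 17-19 years using two cross sectional samples".
- Section 2.5 opens with "This study will recruit 17 to 19 year old males from universities and other sources including sexual health services".
- Section 2.6 (Feasibility) speaks of recruiting the same age group.
- Section 2.7 defines the primary outcome as a change in prevalence "among 17-19 year old men in the two time periods", with 200 males per period and 400 males in all.
- The note to the age-by-year table at the end of the document says "The boxes with hatched lines indicate the age range of boys who will be recruited in Period 1" and goes on to period 2 in the same way. The shading itself is not visible in the text available for this review.

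**The concern.** An age rule needs a reference date, and this one has a four-year window. Taken literally, a man who was 19 in January 2014 still qualifies in 2017, and a boy who turns 17 in 2017 qualifies in 2014. Age matters here because it determines both sexual exposure and whether a man was offered vaccine, and the whole comparison rests on period 1 men being mostly unoffered and period 2 men mostly offered.

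Re-enrolment looks like a second threat. The periods adjoin and may draw on the same universities and clinics, and the exclusion list does not mention earlier participation. Shared men would make the two samples dependent. If the repeats came mainly from men never offered vaccine, they would also dilute period 2.

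**Working it through.** **The plan's own figure.** The intervals in section 2.7 are Wilson intervals with continuity correction. For 5% and n = 200 (z = 1.96, z² = 3.84):

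- Lower = [2np + z² − 1 − z√(z² − 2 − 1/n + 4p(nq + 1))] / [2(n + z²)] = (22.84 − 12.40)/407.68 = 0.0256.
- Upper = [2np + z² + 1 + z√(z² + 2 − 1/n + 4p(nq − 1))] / [2(n + z²)] = (24.84 + 12.95)/407.68 = 0.0927.

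Both match the table, as do the other nine cells. None of these figures depends on when age is assessed.

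**What the footnote can mean.** Being 17-19 throughout the window is impossible, because a three-year age band cannot cover four years. Two readings remain.

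1. Aged 17-19 at some time in the window. Births from 2 January 1994 (still 19 on 1 January 2014) to 30 December 2000 (17 on 30 December 2017) qualify. Possible ages are 13-21 in period 1 and 15-23 in period 2.
2. Aged 17-19 when taking part, within the window. Ages are 17-19 in both periods.

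Only the second agrees with sections 2.3, 2.6 and 2.7, the opening of 2.5 and the age-by-year table note.

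**What depends on the reading.** Section 2.2 gives the oldest offered age as 16, 17, 18 and 19 in 2014 to 2017, which corresponds to birth year 1998 onward. Give each age-by-year cell equal weight.

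- Reading 2: in period 1 only 17-year-olds in 2015 were offered vaccine, 1/6 (17%). In period 2 all but 19-year-olds in 2016 were offered, 5/6 (83%).
- Reading 1, with even recruitment over birth years 1995 to 2000: 3/6 (50%) in both periods, so the contrast vanishes. This is an extreme bound.

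**Overlap under the intended age rule.** The footnote is not its cause: a man aged 17 in 2014 is 19 in 2016 under a correct rule too. By calendar-year cell:

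| Period 1 cell | Eligible again as | Offered vaccine |
|---|---|---|
| 17 in 2014 | 19 in 2016 | no |
| 18 in 2015 | 19 in 2016 | no |
| 17 in 2015 | 18 in 2016 or 19 in 2017 | yes |

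That is 3 of 6 cells. Never-offered men make up 2 of the 3 cells, but 2 of the 4 chances to re-enter. With exact ages uniform on 17-20 and sampling dates uniform, about 67% of period 1 men are under 20 when period 2 opens, and about 35% on a random period 2 date. These are shares eligible, not shares expected to return.

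**Effect of repeats on precision.** With m repeat men and within-man correlation ρ,

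Var = p₁q₁/n + p₂q₂/n − 2mρ√(p₁q₁p₂q₂)/n².

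Assume p₁ = 0.10, p₂ = 0.05 and n = 200:

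- m = 0: √(0.00045 + 0.0002375) = 0.0262.
- m = 50, ρ = 0.1: √(0.0006875 − 0.0000163) = 0.0259.
- m = 50, ρ = 0.5: √(0.0006875 − 0.0000817) = 0.0246.

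Positive correlation reduces the true standard error, so an analysis that ignores the overlap gives intervals that are slightly too wide.

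**Swab timing.** With ages uniform over the three-year band, a delay of d months between recruitment and swab takes d/36 of men past their twentieth birthday, and none by more than d months. The birth cohort, and hence the offer of vaccine, does not change.

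**The case for a change.** The strongest case for a change is that the footnote sits on the operative criterion, and six ethics committees are listed, so several sites must apply the same words. If some applied them literally, the contrast in vaccine offer would weaken, at the extreme from 17% versus 83% to nothing. Repeats could also push one way: the 2016 19-year-olds are the only never-offered cell in period 2, and two of the three re-eligible cells feed it. If 40 of the 200 period 2 men were repeats spread evenly over those three cells, and the rest were spread as designed, the offered share would be (160 × 5/6 + 40 × 1/3)/200 = 73% instead of 83%. Writing the rule down would cost almost nothing.

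Part of this stands. The footnote is loosely worded, and no sentence says that a man may take part only once. The rest does not carry the point. Literal use of the footnote would contradict several other statements in the same plan. The figure of 40 repeats is hypothetical, since the documents give no re-enrolment rate. If repeats are counted by chance of re-entry, the same sum gives (160 × 5/6 + 40 × 1/2)/200 = 77%. The 2016 19-year-olds already belong to period 2 by design, so repeats dilute it only by over-representing that cell. Such dilution would pull the comparison towards no change and would not create a fall.

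**Conclusion.** No change follows. The age footnote is ambiguous, but the criterion it qualifies and the statements in sections 2.3, 2.5, 2.6 and 2.7 lead an investigator to enrol men who are 17-19 when recruited in each period. The questionnaire records age and vaccination history, so an off-age man could be identified at analysis. Two cross-sectional samples totalling 400 males would be understood as 400 different men. Writing down the date of assessment and a one-enrolment rule would record what the plan already implies, without correcting a result it would otherwise get wrong.

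If 50 men did enrol twice, the standard error would move from 0.0262 to no lower than 0.0246, in the conservative direction. This rests on assumed prevalences of 10% and 5% and a within-man correlation of 0.1 to 0.5. The offered shares of 17% and 83% assume equal recruitment per age-year cell. The conclusion would differ only if sites actually recruited across the full birth range of the literal footnote, and nothing in the documents suggests that they would.

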2.6 Study duration

Timelines

This study will require 4 years to complete:

January 2014 – December 2015: approval of study and recruitment in period 1.

January 2016 – December 2017: recruitment during period 2, analysis and reporting.

Feasibility

Our group has a track record of successfully recruiting specific populations that are hard to reach for STI research. We have established strong links with several universities and institutions across Victoria from which 17-19 year old males could be recruited without difficulty and also have a network of clinical sites from which to recruit including the Melbourne Sexual Health Centre.

2.7 Statistical analysis

The primary outcome of interest will be the change in prevalence of quadrivalent vaccine types (6, 11, 16 and 18) among 17-19 year old men in the two time periods. The study will also provide data on the change in prevalence of non-vaccine types.

The required sample size for each year is dependent upon the expected prevalence of genital HPV and affects the precision of the prevalence estimates (95% confidence intervals, CI) in the two cross sectional samples. Different prevalence rates and 95%CI are shown for various sample sizes in Table 1.

Table 1: Estimated 95% confidence intervals for differing HPV prevalent rates and sample sizes

HPV prevalence rate (%)	Sample size (persons)				
	100	200	300	400	500
5	0.0186-0.1183	0.0256-0.0927	0.0293-0.0829	0.0316-0.0774	0.0333-0.0739
10	0.0516-0.1804	0.0637-0.1523	0.0695-0.1411	0.0732-0.1347	0.0758-0.1305

Previous estimates of HPV infection have been determined by investigators in our group for females but are not available for males.⁴ A sample size of 200 males in each of the two periods would provide reasonable confidence intervals around expected prevalence rates for individual HPV types. This would require a total of 400 males for the entire four year study.

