This means that by 2014, 2015, 2016 and 2017, the oldest cohort of males to have been offered vaccination as part of the Victorian program will be aged 16, 17, 18 and 19 years respectively. The age of boys who will have been offered vaccination by year from 2013 through to 2017 is shown in Table 1. In period 1 (2014-2015), 200 boys will be recruited. The same number, 200, will be recruited in period 2 (2016-2017).

Significance of study outcomes

As Australia is the first country to implement a universal male vaccination program we have the opportunity to be among the first to demonstrate a fall in HPV prevalence among males as a result of male vaccination. While there is

evidence that the prevalence of genital warts among males in Australia has fallen as a result of female only vaccination, falls in the prevalence of HPV infection including high risk HPV types among males in response to universal male vaccination have not thus far been documented in any country but is expected to occur.⁵

[figure not shown]
This would provide evidence and argue for the introduction of universal male HPV vaccination programs in countries which have already introduced universal vaccination of females.

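### Section 2.7 names no adjustment for the change between two non-probability samples, and nothing readable keeps their source, site or age mix alike, so a large shift in mix could create a fall or hide part of one

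*Combined protocol and SAP*

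**What the plan says.** Section 2.7 gives the primary outcome as a change between periods ("The primary outcome of interest will be the change in prevalence of quadrivalent vaccine types") and adds that "The study will also provide data on the change in prevalence of non-vaccine types". It names no effect measure, test, model, stratification or covariate. Its only statistical figures are confidence intervals for a single prevalence, from which 200 men per period are chosen.

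On recruitment, section 2.5 says: "This study will recruit 17 to 19 year old males from universities and other sources including sexual health services". Section 2.6 says that the investigators "also have a network of clinical sites from which to recruit including the Melbourne Sexual Health Centre". Section 2.5 describes a "self-testing kit that is either given to participants attending services or posted out if recruitment is via advertising", so the route of entry must be known for each man when the kit goes out. It is not said to be kept as an analysis variable.

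The questionnaire in 2.5 records age, education and sexual history, including "age at first sex; number and gender of sexual partners over different time periods". None of these is tied to an analysis.

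Section 2.3 describes the period 1 prevalence as "a prevalence that reflects herd immunity from pre-existing vaccination of females". Section 2.2 gives the reach of the male programme for each calendar year of the study: "the oldest cohort of males to have been offered vaccination as part of the Victorian program will be aged 16, 17, 18 and 19", one age for each year in turn from 2014 to 2017.

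**The concern.** Section 2.1 sets a causal aim: the fall is to be credited to the male programme. The evidence is a comparison of two separate groups of volunteers. Men attending a sexual health service may well differ in HPV prevalence from men answering a university advertisement. If the share of each differs between periods, the crude change mixes that shift with any vaccine effect.

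Age acts in two ways. Prevalence may differ between ages 17 and 19, and on the protocol's own schedule the share of men offered vaccine depends on single year of age and on calendar year within each period.

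A fall could thus be reported that is partly case mix, or a real fall could be diluted. With no adjustment set named, covariates could be chosen after the data are seen.

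**Working it through.** **1. The plan's own figures.** The Wilson interval with continuity correction reproduces all ten cells of Table 1 in section 2.7. For p = 0.05, n = 200, z² = 3.8415:

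- Lower: [20 + 3.8415 − 1 − 1.96·√(3.8415 − 2 − 0.005 + 0.2·191)] / 407.683 = 0.0256.
- Upper: [20 + 3.8415 + 1 + 1.96·√(3.8415 + 2 − 0.005 + 0.2·189)] / 407.683 = 0.0927.

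The table is sound, but it describes one sample and not the change between two.

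**2. Inputs for the mix calculation.** From the protocol: 200 men per period. Assumed, because 2.7 says no male estimates exist: prevalence 12% in clinic recruits and 5% in others, and every clinic share below.

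**3. Crude prevalence** = share × 12% + (1 − share) × 5%, halved in period 2 where a true halving is assumed.

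- No effect, 60% to 30%: 0.6·12 + 0.4·5 = 9.2%; 0.3·12 + 0.7·5 = 7.1%; false fall 2.1 points.
- No effect, 50% to 40%: 8.5% and 7.8%; 0.7 points.
- Halving, 30% to 60%: 7.1% and 9.2/2 = 4.6%; a 35% fall instead of 50%.

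For scale, the half-width 1.96·√(0.092·0.908/200 + 0.071·0.929/200) is 5.36 points. The two false falls are 39% and 13% of it.

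**4. Chance that the 95% CI shows a fall.** For counts x and y in periods 1 and 2, the CI for the ratio is exp[ln(y/x) ± 1.96·√(1/x + 1/y − 2/200)]. The exact column sums binomial probabilities over all (x, y) with upper limit below 1. The last two columns are a simulation (4000 runs per case; robust Poisson with period, age, source and partners). It assumes that all clinic men and 70% of others are sexually experienced, and that risk rises with partners and age.

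| True effect | Clinic share | Prevalences | Crude, exact | Crude, simulated | Adjusted, simulated |
|---|---|---|---|---|---|
| None | 60% to 30% | 9.2%, 7.1% | 10.4% | 9.9% | 1.6% |
| None | 55% to 35% | 8.85%, 7.45% | 6.5% | 6.8% | 2.2% |
| None | 50% to 40% | 8.5%, 7.8% | 3.9% | 3.8% | 2.0% |
| None | no shift (exact: 45%) | 8.15%, 8.15% | 2.2% | 2.4% | 2.4% |
| Halving | 30% to 60% | 7.1%, 4.6% | 16.4% | 16% | 38% |
| Halving | 40% to 50% | 7.8%, 4.25% | 29.4% | 28% | 37% |
| Halving | no shift (exact: 45%) | 8.15%, 4.075% | 37.3% | 38% | 38% |

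The 37% reference holds the share at 45%, midway between 30% and 60%. Holding it at 30% (7.1% and 3.55%) gives 32%, so part of the drop to 16% reflects the choice of reference.

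**5. Other assumed prevalences.** With 7% and 3%: no effect, 60% to 30%, crude 6.1% against adjusted 1.9%; 50% to 40%, 2.5% against 1.9%; halving, 30% to 60%, 8% against 22%. With 15% and 5%, no effect, 70% to 30%: 12% and 8%, and about a 27% chance of a false fall by normal approximation. Age alone, assuming 5%, 10% and 15% at 17, 18 and 19: moving from 20/30/50 to 50/30/20 gives 11.5% and 8.5%, and about a 17% chance.

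**6. Share offered vaccine, Victorian schedule only.** Counting a whole age-year as offered, men aged 17-19 are offered as follows: none in 2014, age 17 in 2015, ages 17-18 in 2016, all in 2017.

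- Equal ages and years: period 1 = 0.5·0 + 0.5·(1/3) = 17%; period 2 = 0.5·(2/3) + 0.5·1 = 83%.
- Recruitment only in 2015 and 2016, equal ages: 33% and 67%.
- Equal years, ages 50/30/20 then 20/30/50: 0.5·0.5 = 25% and 0.5·0.5 + 0.5 = 75%. The reverse order gives 10% and 90%.

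If offered ages had 0.4 times the risk, and baseline risk were equal across ages, the expected ratio is (1 − 0.6·0.833)/(1 − 0.6·0.167) = 0.56 with equal years, but (1 − 0.6·0.667)/(1 − 0.6·0.333) = 0.75 with 2015 against 2016. Covariate adjustment does not remove this difference; it has to be reported.

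**7. Non-vaccine types as a check.** If they are 2.5 times as common (assumed), a 60% to 30% shift gives 23.0% and 17.75%, significant in about 26% of studies. A 50% to 40% shift is significant in about 7%.

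**The case against.** The strongest reply is that the harm is conditional. No passage says that recruitment will change; 2.5 and 2.6 describe one set of sources for the whole study. Eligibility is the same in both periods, the age band is three years, age and sexual history are collected, and non-vaccine types will be reported. A 10-point shift in clinic share barely moves the false-fall chance. Imprecision at 200 per period is the larger problem: even with a stable mix, a true halving is shown in only about 37-38% of studies under the 12% and 5% assumption.

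Most of this stands, and it limits the point to large shifts. It does not remove the point. Common eligibility fixes neither source nor age within 17-19, the covariates have no stated use, and non-vaccine types have no stated role and low power as a check.

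Four stronger readings are tempting and not supported:

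- That the samples will differ. The documents give neither the size nor the direction of any shift.
- That adjustment would necessarily be chosen after the data are seen. The protocol does not rule out a later plan fixed before analysis; it only leaves the choice open.
- That the 17% and 83% shares describe the study. They apply Victoria's schedule, assume equal recruitment by year, and ignore the other states where 2.5 (Ethical approval) plans recruitment. Section 2.6 places approval inside period 1 and reporting inside period 2, so recruitment could cluster in 2015 and 2016.
- That one particular model is required. Several methods would do.

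**Conclusion.** The concern holds for a large shift in mix. As written, the plan yields a crude contrast between two volunteer samples, with nothing readable to keep them comparable. The section 2.4 flowchart and the shading of the age table are not readable, so the conclusion is limited to the text.

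Under the 12% and 5% assumption, a 30-point change in clinic share raises the false-fall chance from a nominal 2.5% to about 10%, or lowers the chance of showing a true halving to about 16% (32-37% with a stable share, depending on the reference). A 10-point change gives about 4% for a false fall, though it still takes something from a true one (about 29%). The range in steps 4 and 5 shows how far these figures depend on assumed prevalences. The point should be fixed, with medium confidence: the omission is clear from the text, but its consequence cannot be sized from the documents.

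**What to change.** 1. In 2.5, keep recruitment source (university, advertising, sexual health service), state or site, and recruitment date as variables for every man. Aim for a similar source and single-year age mix in both periods.
2. In 2.7, keep all men aged 17-19 as the population. Beside the crude change, pre-specify a period 2 against period 1 prevalence ratio with its 95% CI, adjusted for age, source (clinic or other) and number of partners in one named time window. Robust Poisson regression is suitable; standardisation to the period 1 mix is an acceptable alternative. Name in advance a reduced set (age and source) for use if events are few.
3. Report recruitment by calendar year, age and state in each period. State that the ratio averages over ages and years with different shares offered vaccine.
4. Report the change in non-vaccine types as a low-power check on case mix. State that selection within sources and continuing herd effects of female vaccination are not removed.

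The cost is a few retained fields and a few sentences. In simulation the standard error of the log ratio rose by 0-3% (0.352 to 0.360 for a 60% to 30% shift; 0.447 to 0.459 for 30% to 60% with halving). The main limit is sparse events. At 7% and 3% with halving and a 30% to 60% shift, 200·(0.042 + 0.027) = 13.8 events are expected, about 3.45 for each of four terms. With events that few, up to 58 of 4000 fits failed, which is why the reduced set should be named beforehand.
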